4.3 Subject Recruitment, Enrollment and Screening

Subjects will be contacted by letters, email and telephone calls (maximum number of contact attempts with subject will be 3). Copies of the letters, email scripts and telephone scripts will be submitted to IRB.

At the time of enrollment the investigator or personnel involved in recruitment will address the following:

Amount of time needed for reading or reviewing the consent document Amount of time needed for the prospective subject to make a decision

The location or methods of communicating and the related privacy needs for the initial and on-going discussions.

The need for including a medical interpreter, Legally Authorized Representative, family member(s), witness, or advocate who may need to be present and observe the discussions within the informed consent process.

The screening procedure will involve the following:

- Evaluation and documentation of inclusion/exclusion criteria
- Blood draws to measure labs (see table 1)
- Serum pregnancy test unless postmenopausal
- DEXA scan, Data from DEXA scans conducted in the CRTU for other protocols within a 3 month time period may be used in place of repeating the scan in order to reduce radiation risk.
- CT scan.*
- Meeting with the registered dietitian to discuss food preferences, food allergies, etc. for the three-day meal plans.
- Maximum physical exertion level will be examined. This will include periodic monitoring of heart rate and blood pressure. An EKG will also be a part of this test.

* Single slice abdominal L2-L3 CT scans conducted in a previous 3 month window, may be used in place of repeating the CT scan.

4.3.1 Early Withdrawal of Subjects

4.3.2 When and How to Withdraw Subjects

Subjects must be withdrawn from the study for any of the following reasons:

- Withdrawal of informed consent
- Pregnancy
- If the investigator concludes that it would be in the subject's best interest for any reason

Subjects may voluntarily withdraw from the study for any reason at any time.

If withdrawal occurs for any reason, the investigator will document the reason for withdrawal in the source notes.

4.3.3 Data Collection and Follow-up for Withdrawn Subjects

Subjects who withdraw after enrollment will be replaced to complete the study.

5 Study Drug

5.1 Description

The investigational product to be studied will be an infusion of nicotinic acid (niacin) or saline. The chemical formula is C₆H₅NO₂. It is a white, crystalline, powder that is reconstituted for intravenous infusion. It is soluble in water.

A. Mechanism of Action

As B complex vitamins, niacin and niacinamide have identical physiological effects. However, these vitamins differ in some of their actions. Niacin produces peripheral vasodilation and flushing, an effect that generally does not occur with niacinamide. Niacinamide is formed in vivo from metabolism of niacin. Niacinamide is an essential precursor of nicotinamide adenine dinucleotide (NAD) and nicotinamide adenine dinucleotide phosphate (NADP), which are the physiologically active forms of niacin. Serving as coenzymes for several dehydrogenases, NAD and NADP are functional groups of electron-transfer agents active in cellular respiration, glycolysis, and lipid synthesis. When taken in amounts considerably greater than needed to meet vitamin requirements, niacin causes a partial suppression of the release of free fatty acids from adipocytes.

Niacin can lower serum triglyceride and LDL-cholesterol concentrations. Rate of hepatic TG synthesis are decreased and thereby decreased VLDL. Subsequent clinically lowered apo B and LDL concentrations are found (81).

B. Pharmacokinetics

Absorption

Nicotinic acid undergoes rapid first-pass hepatic metabolism after oral ingestion, which we will avoid by infusing it intravenously. Niacin concentrations in the systemic circulation are dose-dependent.

A) Bioavailability – intravenous – 100%

B) Effects of Food – none known with intravenous niacin

Distribution

Nicotinic acid is widely distributed and is concentrated in liver, spleen, and adipose tissue.

Metabolism

When administered orally the pharmacokinetic profile of niacin is complicated due to extensive first-pass metabolism. The profile is dose-rate specific and, at the doses used to treat dyslipidemia, saturable. In humans, one pathway of metabolizing niacin is through a simple conjugation step with glycine to form nicotinuric acid (NUA). NUA is excreted in the urine, although there may be a small amount of reversible metabolism back to niacin. The other metabolic pathway results in the formation of nicotinamide adenine dinucleotide (NAD). It is unclear whether nicotinamide is formed as a precursor to, or following the synthesis of, NAD. Nicotinamide is further metabolized to at least N-methylnicotinamide (MNA) and nicotinamide-N-oxide (NNO). MNA is further metabolized to two other compounds, N-methyl-2-pyridone-5-carboxamide (2PY) and N-methyl-4-pyridone-5-carboxamide (4PY). The formation of 2PY appears to predominate over 4PY in humans. The activity of these metabolites is unknown.

Excretion

Following single and multiple doses, approximately 60 to 76% of the niacin dose administered orally is recovered in urine as niacin and metabolites; up to 12% was recovered as unchanged niacin after multiple dosing. The ratio of metabolites recovered in the urine was dependent on the dose administered. Niacin is excreted as nicotinuric

acid in urine after conjugation with glycine. Whether the same distribution of metabolites in the urine occurs with intravenous as with oral administration is unknown.

5.2 Treatment Regimen

Subjects will receive a titrated dose starting from 0.6 mg/min to a maximum of 2.8 mg/min (likely needed dose = 1.4 mg/min) or 0.9% NaCl for 12 hours.

5.3 Method for Assigning Subjects to Treatment Groups

Subjects will first receive niacin and for the second study they will receive intravenous saline as the placebo.

Preparation and Administration of Study Drug

Nicotinic acid will be received in powder form and compounded at Research Pharmacy following Compounding Procedures and an approved compounding formula sheet, for intravenous administration which runs in a Baxter infusion pump model Sigma Spectrum. The drug will be aliquoted in single dose amber vials of 10 mL each and refrigerated at a temperature of 2-8°C.

5.4 Subject Compliance Monitoring

We are not expecting non-compliance as the drug administration is a constant monitored intravenous infusion. In cases where a subject requests to stop study drug, it will be recorded and reported as a note to file or a protocol deviation.

5.5 Prior and Concomitant Therapy

The following medications will be withheld 3 days prior to beginning of the study:

- Participants with Type 2 Diabetes on insulin will have their long-acting insulin replaced with a short-acting insulin.

5.6 Packaging

Contents of kits/boxes associated with labelling: The study drug or saline/placebo is labelled with a patient specific label by the RESEARCH pharmacy. This label shall bear the statement "Caution: New Drug--Limited by Federal (or United States) law to investigational use."

5.7 Masking/Blinding of Study

This study is not a blinded study.

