1.5 Risks and Benefits

Radiation: Radiation exposure from the studies supported by this grant include the radiation from the dual energy x-ray absorptiometry, and computed tomography scans of the abdomen.

Blood sampling: Blood samples are collected from an indwelling intravenous catheter for this study. Bruising can occur with venipuncture, as can fainting.

Infusion of substrates: We will infuse minute quantities of glucose and palmitate that are labeled with stable isotopes as part of these studies. The quality assurance plans for these compounds are reviewed and approved by the Mayo Clinic Radioactive Drug Research Committee as the designated representative of the FDA. We will also infuse insulin intravenously and give local anesthetics for the tissue biopsies. The insulin is infused using clinical safeguards as well as research pharmacy safeguards under an IND exemption from the Mayo IRB.

Adipose and muscle biopsies: The risks of these procedures include pain, hematomas, bruising, infection, and scarring of the biopsy site.

Insulin infusion: The risk of insulin infusion is hypoglycemia.

Niacin: the risk of niacin infusion is flushing, pruritus, nausea or vomiting.

2 Study Objectives

Primary Objective

To assess the effect of overnight suppression of FFA with intravenous niacin on trafficking of FFA into intramyocellular ceramides and/or DG

Secondary Objective

To assess the effect of overnight suppression of FFA with intravenous niacin on insulin signaling and insulin-stimulated muscle glucose uptake

3 Study Design

This study is a non-randomized, niacin vs. saline control trial of the effects of niacin on intracellular fatty acid trafficking in insulin resistant states. Subjects will be screened at outpatient clinic visit appointments and interested qualified subjects will be consented and offered participation in this trial. Once consent has been obtained baseline values will be established and subjects will begin treatment and follow-up for up to the next 8 weeks.

A final evaluation and collection of lab samples will be conducted at the end of the study.

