As part of the screening for these studies a medical history and physical examination will be performed, blood tests and body composition measurements will be made. None of the research data will be entered into the Mayo Electronic Medical Record. Any paper records that are generated are kept in [name] laboratory, which is locked at all times to prevent hallway entry. Because it often takes several months from the initial volunteer contact until the studies are complete, and because we need to communicate with multiple units (Radiology, Nuclear Medicine, Mayo CTSA CRTU, etc.) over the course scheduling, it is not possible to de-identify paperwork immediately. The paperwork with patient identifiers is kept in a locked room when

not in use. Whenever possible the paper records generated will be such that once the study is complete the identifiers can be removed. A paper matching the subject name and other identifying information with the subject code should be kept in a separate place from the study information. No information will be given to anyone without permission from the subject. If samples are sent outside Mayo for analysis they are de-identified per Mayo Biospecimens Committee rules.

Data Quality Assurance

- 1) Description of Plan for Data Quality and Management: The PI will review all data collection forms on an ongoing basis for data completeness and accuracy as well as protocol compliance. A statement reflecting the results of the review will be sent to the NIDDK in the annual report (non-competing continuation). Although there are additional reports to be produced by the study coordinator as a result of this DSMP, there are no substantive changes to the study protocol that might require review by the NIDDK.
- 2) Frequency of Review. The personnel and frequency of data review in these studies varies depending upon the source and type of data. The frequency of data review for this study is summarized in the following table.

Data type	Frequency of review	Reviewer
Subject accrual (adherence to protocol regarding demographics, inclusion/exclusion)	Monthly	Study coordinator, research fellow and Principal Investigator
Adverse event rates (injuries)	Quarterly	Study coordinator, research fellow, Principal Investigator and Endocrine Research Committee as independent monitor
Out of range research laboratory data	As results become available	Research fellow and Principal Investigator*

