Overview of data collection as regards statistical power implications of drop outs and missing data	Yearly	Research Fellow and Principal Investigator

* the research data generated by these studies is unique, entirely novel and requires profound expertise/experience to identify analytical, experimental or other research laboratory problems that may have arisen.

B. Subject Accrual and Compliance

1) Measurement and reporting of subject accrual, adherence to inclusion/exclusion criteria

Review of the rate of subject accrual, adherence to inclusion/exclusion criteria will occur during the weekly meetings [name] has with the research fellow and/or study coordinator working on each protocol. In addition to these reviews [name] will conduct an informal quarterly progress report with the fellow in charge of each protocol where more comprehensive overall progress is discussed and we determine whether changes need to be made to our recruitment strategy. Given that small numbers of volunteers are recruited for each protocol and some are linked to clinical patient care populations we will track whether overall participation in the 2 different projects combined include participants that meet our ethnic diversity goals.

2) Measurement and reporting of participant compliance to treatment protocol- the only compliance issues relate to volunteers returning for the second study.

Data Clarification Process

A report will be run in Excel to identify missing elements in the data capture. A designated study team member will make corrections in the data and the principle investigator will verify.

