Out of range research laboratory data	As results become available	Research fellow and Principal Investigator*
Overview of data collection as regards statistical power implications of drop outs and missing data	Yearly	Research Fellow and Principal Investigator

* the research data generated by these studies is unique, entirely novel and requires profound expertise/experience to identify analytical, experimental or other research laboratory problems that may have arisen.

B. Subject Accrual and Compliance

- 1) Measurement and reporting of subject accrual, adherence to inclusion/exclusion criteria Review of the rate of subject accrual, adherence to inclusion/exclusion criteria will occur during the weekly meetings [name] has with the research fellow and/or study coordinator working on each protocol. In addition to these reviews [name] will conduct an informal quarterly progress report with the fellow in charge of each protocol where more comprehensive overall progress is discussed and we determine whether changes need to be made to our recruitment strategy. Given that small numbers of volunteers are recruited for each protocol and some are linked to clinical patient care populations we will track whether overall participation in the 2 different projects combined include participants that meet our ethnic diversity goals.

2) Measurement and reporting of participant compliance to treatment protocol – The weight loss intervention provided as part of these studies is purely voluntary and no compliance issues are anticipated.

C. Justification of Sample Size – We used published data regarding the improvement in an insulin sensitivity from a study that used Acipimox to determine that 10 subjects/group will be sufficient to detect a clinically meaningful change in insulin action with 90% power at a P of <0.05.

D. Stopping Rules - Because this is not a treatment studies per se, but instead one physiological measurements that take advantage of a clinical treatment protocol with its own monitoring, there is no stopping rule based on interim data analysis clearly demonstrates an effect. This study will be stopped prior to its completion if: (1) adverse effects that significantly impact the risk-benefit ratio have been observed; (2) study recruitment or retention becomes futile; (3) any new information becomes available during the trial that necessitates stopping the trial; or (4) other situations occur that might warrant stopping the trial.

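### Out-of-range research assay values are judged by the fellow and investigator with nothing that hides the study day; coding stored muscle samples by visit would reduce this uncontrolled risk of bias

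*Combined protocol and SAP*

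**What the plan says.** - **Masking.** Section 5.7 is one sentence: "This study is not a blinded study". It does not separate the infusion from the laboratory.
- **Order.** Section 5.3: "Subjects will first receive niacin and for the second study they will receive intravenous saline as the placebo". Section 3 agrees: "This study is a non-randomized, niacin vs. saline control trial". The Study Summary calls the study randomized and Section 7.2 refers to randomization. That is a separate inconsistency, and this point does not depend on it.
- **Review of assay values.** The tables in Sections 9.3 and 10.1 (V.A) have a row for "Out of range research laboratory data". It is reviewed as results become available, by the research fellow and principal investigator only. The Endocrine Research Committee is named as independent monitor for adverse event rates, not for this row.
- **Criterion.** The footnote to that row says the research data are novel and that their review "requires profound expertise/experience to identify analytical, experimental or other research laboratory problems that may have arisen". No numerical range, rerun rule or exclusion rule follows.
- **Corrections.** Section 9.3: "A designated study team member will make corrections in the data and the principle investigator will verify".
- **Coding.** The coding described protects the participant's identity, for example "If samples are sent outside Mayo for analysis they are de-identified per Mayo Biospecimens Committee rules". No code hides visit, date or treatment.
- **Expected direction.** Section 1.1 predicts that niacin will lower trafficking of plasma FFA into ceramides and/or DG and improve insulin signaling and glucose disposal.

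**The concern.** The infusion may be hard to mask, but the muscle assays need not be run or reviewed with the day visible. Incorporation of palmitate into muscle triglyceride, DG and ceramide is the primary endpoint (Section 3.4), and insulin signaling is secondary (Section 3.5). Deciding whether an odd value reflects a laboratory fault is a judgement. Here it is left to people with a stated expectation, without a written rule and without any barrier to their knowing the day.

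If a value that goes against the hypothesis is more readily called a fault than one that agrees with it, the niacin-saline difference moves in the expected direction. Section 7.2 allows analysis of all available data when missing values are few and look random, so a rejected value could simply leave the paired comparison. With 10 participants per group, a single pair carries weight.

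The fixed order adds a second problem. Assay drift between visits would be confounded with treatment unless both visits of a participant are assayed together, and the documents do not say that they are.

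**Working it through.** **The plan's own figure.** The plan gives no figure on this point. Its one worked design figure, in Section 7.1, is 90% power for a 10% change with 5 subjects. Reading the ~5% reproducibility as the SD of the paired difference, the noncentrality is (10/5) × √5 = 4.47 on 4 degrees of freedom, and power at two-sided 0.05 is 90.9%. The figure reproduces, and coding samples would not change it.

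**Inputs for the illustration.**
- 10 pairs per group, 20 in all (Section 3.2).
- Saline day against niacin day by paired t-test (Study Summary).
- My assumptions: no true effect, normal differences, and in every trial the pair most contrary to the hypothesis is discarded. The documents give no discard rate.

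**Shift in the mean.** Dropping the most contrary of n pairs moves the expected mean by E[largest of n standard normals] / (n − 1), in SDs of the paired difference:
- n = 10: 1.54 / 9 = 0.17 SD
- n = 20: 1.87 / 19 = 0.10 SD
- n = 5 (one sex within one group, given the sex-specific analysis in Section 7.1): 1.16 / 4 = 0.29 SD

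**False positives by simulation** (40,000 and 200,000 runs; the ranges span the runs):

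| Pairs | Discarded | Favourable direction (nominal 2.5%) | Two-sided (nominal 5%) |
|---|---|---|---|
| 10 | 1, day known, most contrary | 8.5 to 8.8% | 9.8 to 10.1% |
| 10 | 2, day known, most contrary | about 18.7% | about 19.4% |
| 20 | 1, day known, most contrary | 7.5 to 7.7% | 8.8 to 9.0% |
| 10 | 1, day hidden | 2.5 to 2.6% | 5.0 to 5.3% |

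In the day-hidden row the discarded pair is the one with the largest gap of unknown sign, or the one holding the most extreme single value. The mean shift is zero.

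**Range over the unknown discard rate.** If such a discard happens in a fraction f of trials, independently of the rest of the data, favourable-direction error for n = 10 is about 2.5% + f × (8.7% − 2.5%). That is 2.5% at f = 0, 4.1% at f = 0.25, 5.6% at f = 0.5 and 8.7% at f = 1.

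**How the code is built matters.** If every participant's two days carry the same pair of labels, a reviewer can still see the differences on a common sign and drop the one furthest from their mean. With 10 pairs that gives no shift but a two-sided error of about 13%. The label must therefore be assigned at random for each participant, and the rejection rule written beforehand.

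**The case against.** **Stronger readings the documents do not support.** A reader might infer that the reviewers know which day each value comes from and do reject or rerun values. The documents say neither. They give a data type, a review frequency, the reviewers and a footnote about recognising laboratory problems. That the day is visible is a fair inference from an open study with fixed order. That values are discarded is only a possibility. It would also be wrong to take 8.5% as the trial's error rate: it assumes one maximally unfavourable discard every time, whether or not any value was out of range.

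**Existing safeguards.** Section 9.3 requires missing data to be explained and errors to be struck through. Section 7.2 examines the pattern of missing data for systematic bias. Section 10.2 opens the data to audit. These make silent discarding harder, but none hides the day when the judgement is made.

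**Limits of coding.** These objections largely stand.
- Niacin is meant to lower plasma FFA, so plasma FFA and palmitate may reveal the day. DG and ceramide enrichment is expressed relative to plasma palmitate (Section 7.2).
- Overnight FFA results guide the infusion in subsequent studies (Sections 3.1 and 6.2), so they cannot be held back.
- Staff adjust the clamp glucose infusion every 10 minutes (Section 6.2), so glucose disposal cannot be masked through sample codes.
- Adipose tissue goes straight to the laboratory for collagenase digestion (Section 6.2) and cannot be stored until the second visit. Cell size and immunohistochemistry are also not among the endpoints in Sections 3.4 and 3.5.

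They narrow the remedy to stored muscle samples and later adipose readouts. They do not remove the case for it.

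**Conclusion.** The concern holds as an uncontrolled risk of bias in the muscle assays, not as bias shown to have occurred. It rests on four features of the text: no masking, a fixed order, review by the fellow and investigator alone on judgement without a numerical criterion, and no code that hides the day.

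The upper illustration for one discard among 10 pairs is a 0.17 SD shift and favourable-direction error of about 8.5% instead of 2.5%. It falls towards 2.5% as the unknown discard rate falls. It assumes normal differences and a paired t-test, and it does not model reruns. A reader might also infer that coding would remove the bias. It would reduce it, mainly for muscle DG, ceramide, triglyceride and Akt. For a single-site pilot this is a worthwhile and inexpensive safeguard, not a flaw that invalidates the design.

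**What to change.** Amend Sections 5.7 and 10.1, and the matching text in 9.3:

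1. Label stored muscle samples (DG, ceramide and triglyceride concentration and enrichment; Akt blots) with codes that hide visit number and date from assay staff and from those judging out-of-range values. Assign the codes at random within each participant. The study coordinator, who is not listed as a reviewer of out-of-range values, holds the list.
2. Run both visits of a participant in the same assay batch.
3. Write the range, rerun and exclusion rules beforehand. Make and log every such decision before the code is opened, and judge the muscle values before they are divided by plasma palmitate. Report the analysis with and without any excluded values.
4. Leave outside the code the overnight FFA results used to guide the infusion, clamp glucose and clinical safety results.
5. Process fresh adipose tissue on the day, and code only its later readouts (cell-size images, immunohistochemistry).

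**Cost.** A code list must be kept, and muscle assay results are delayed until after the second visit, about 4 to 8 weeks (day 28 to 56 in the Schedule of Events). The documents give no figure for the staff time. Participant procedures, the infusions and the sample size do not change.
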